7.9.4 Administration and Exposure of Study Drug

Administration of study drug (planned dose level, total dose administered, total volume administered, infusion flow rate, infusion duration, subjects with infusion reactions, and subjects with dose interruptions) will be summarized using descriptive statistics. Infusion flow rate will be calculated as total volume administered ÷ infusion duration. A listing will also be generated.

7.9.5 Cytoreductive Surgery Details and Specimen Collection

Cytoreductive surgery details including the following will be summarized on a patient level using descriptive statistics in the Safety population:

- Duration of surgery
- Suspected PCI score and fluorescence imaging PCI score
- Method of localization

- Number of SOC suspicious nodules collected
- Number of SOC normal specimens collected
- Additional fluorescent areas collected
- Cytoreduction score
- Time spent imaging
- Camera system used

A listing will also be generated.

7.10 Efficacy Endpoint Analyses

Imaging will be assessed on the Efficacy population.

7.10.1 Primary Analyses

7.10.1.1 Analysis of Clinically Significant Events

The number and proportion of subjects with CSEs will be summarized by Group. CSE responders will be summarized, as well as each type of CSE. These summaries will include 95% 2-sided confidence intervals for the proportion of CSEs calculated via Clopper-Pearson method.

A listing of all CSEs by patient will be provided.

7.10.2 Secondary Analyses

7.10.2.1 Analysis of Diagnostic Imaging

The positive predictive value, negative predictive value, sensitivity, and specificity (biopsy level) will be calculated and summarized for each Group. The summary will include the true/false negatives/positive rate and number of specimens. Two-sided 95% confidence intervals will be calculated for each rate via Clopper-Pearson method.

A listing by subject and specimen showing the fluorescence status, pathology result, specimen type (SOC vs. fluorescence), suspicious vs. normal, fluorescence in *in situ* and *ex situ*, and fluorescence measures (MFI, SBR or TBR) will be provided.

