6.3 Surgery and Follow-up Visits (Group 1 and 2)

Procedures at the time of cytoreductive surgery

The following procedures will be performed on the day of surgery:

- Record the patient's vital signs (only if they were abnormal at dosing)

- Obtain blood for routine laboratory tests
- Record all medications being taken, including prescription, over-the-counter, and herbal medications
- Discuss with the patient any new or unexpected changes they are feeling
- Record any AEs

Once the patient is under anesthesia, some procedures will occur that would not normally be part of surgery if the patient were not in this study. The SOC surgical procedures will be allowed to continue with the addition of the steps listed below.

- During SOC resection, the surgeon will select up to 15 (10 suspected tumor and 5 normal) specimens that will be imaged using the intraoperative camera on a section of normal tissue following excision (*Note: NIR camera should not be used to examine the peritoneal cavity at this time*)
 - A total of up to 15 specimens are to be imaged: 5 representative normal pieces of tissue and 10 individual suspected tumor specimens
 - The SOC specimens are to be resected upon the initiation of surgery and imaged on a section of normal tissue (i.e., mesentery) immediately following the collection of all SOC samples
 - The width of the camera's field of view is to be confined to a distance of 10 cm. A surgical ruler is to be placed in frame to control the width of the field of view
 - Note: while there are no specimen size stipulations provided in this protocol, the samples must be able to be imaged within the 10 cm wide imaging window.
 - For samples with multiple nodules, individual nodules should be dissected away from the bulk sample and imaged individually as single specimens.
 - Representative normal sections of tissue should be imaged in an analogous manner
- Samples will be imaged using the NIR camera and fluorescence status and specimen name will be dictated by the surgeon for documentation by the clinical research coordinator in the provided Imaging Workbook
- Once the SOC resection is complete, the surgeon will dictate their completeness of cytoreduction score to the clinical research coordinator for documentation prior to examining the peritoneal cavity with the intraoperative NIR camera in search of additional fluorescent metastatic disease that was missed during SOC

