9.4 Imaging Analysis

Diagnostic performance of pgsitacianine will be assessed at the level of the specimen by calculating the *ex situ* sensitivity, specificity, PPV, and NPV of pgsitacianine in detecting tumor containing tissue. The *ex situ* fluorescence status of collected SOC and pgsitacianine guided specimens will be compared to the histological analyses of the collected specimens (which is used to determine each sample's status as true/false positive/negative). For determining these operating characteristics, consider the following definitions:

- False positive is defined as “fluorescence was observed on the specimen but the specimen was not found to have tumor via histological analysis”.
- False negative is defined as “no fluorescence was observed on the specimen but the specimen was found to have tumor via histological analysis”.

- True positive is defined as “fluorescence was observed on the specimen and the specimen was found to have tumor via histological analysis”.
- True negative is defined as “no fluorescence was observed on the specimen and the specimen was found not to have tumor via histological analysis”.

The number of specimens in each category (each combination of true/false positive/negative), along with the true/false positive/negative rates (and corresponding exact two-sided 95% confidence intervals) will be reported. These rates will be used to determine pegsitacianine’s tumor detection sensitivity, specificity, PPV, and NPV using the following equations:

$$\text{Sensitivity} = \frac{\text{\# of True Positive Specimens}}{\text{\# of True Positive + False Negative Specimens}}$$

$$\text{Specificity} = \frac{\text{\# of True Negative Specimens}}{\text{\# of True Negative Specimens + \# of False Positive Specimens}}$$

$$\text{PPV} = \frac{\text{\# of True Positive Specimens}}{\text{\# of True Positive + False Positive Specimens}}$$

$$\text{NPV} = \frac{\text{\# of True Negative Specimens}}{\text{\# of Tumor Negative + False Negative Specimens}}$$

These rates will be reported along with exact two-sided 95% confidence intervals.

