1. INTRODUCTION

This Statistical Analysis Plan covers the statistical analysis and reporting for the protocol ON-1003 dated 23JUN2021. A detailed list of tables, listings and figures (TLFs) will be supplied in a separate, version-controlled document.

In case of discrepancies between the SAP and the protocol, the SAP will overwrite the protocol with respect to analyses and reporting.

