5.1.2 Diagnostic Imaging Endpoints

Diagnostic performance of pegasitacianine will be assessed by calculating sensitivity, specificity, NPV and PPV of pegasitacianine in detecting tumor containing tissue. The *ex situ* fluorescence status (any fluorescence vs. no fluorescence) of collected SOC and pegasitacianine guided specimens, as well as lymph nodes, will be compared to histological analyses of the collected specimens. Sensitivity and specificity for detecting tumor-containing tissue versus normal tissue

will be evaluated using tissue specimen fluorescence and the corresponding pathological outcomes.

True/false negative/positive definitions are as follows:

- False positive is defined as fluorescence was observed on the sample but the sample was not found to have tumor via pathology.
- False negative is defined as no fluorescence was observed on the sample but the sample was found to have tumor via pathology.
- True positive is defined as fluorescence was observed on the sample and the sample was found to have tumor via pathology
- True negative is defined as no fluorescence was observed on the sample and the sample was found not to have tumor via pathology.

Pegsitacianine sensitivity and PPV will be calculated using the following equations:

$$\text{Sensitivity} = \frac{\# \text{ of True Positive Specimens}}{\# \text{ of True Positive Specimens} + \# \text{ of False Negative Specimens}}$$

$$\text{PPV} = \frac{\# \text{ of True Positive Specimens}}{\# \text{ of True Positive Specimens} + \# \text{ of False Positive Specimens}}$$

Specificity values and negative predictive values (NPV) calculated by the equation below:

$$\text{Specificity} = \frac{\# \text{ of True Negative Specimens}}{\# \text{ of True Negative Specimens} + \# \text{ of False Positive Specimens}}$$

$$\text{NPV} = \frac{\# \text{ of True Negative Specimens}}{\# \text{ of True Negative Specimens} + \# \text{ of False Negative Specimens}}$$

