7.10.3.3 Adjustment for Clustering

There is potential for within-subject correlation to bias our estimates of pegasitacianine's diagnostic accuracy. To assess this issue, an ROC curve will be constructed from a mixed model that clusters specimens by the subject they originated from. We will compare the AUC of the mixed effects ROC curve to the standard ROC curve to assess if within-subject correlation is causing significant bias in our analyses. If it is determined that significant bias has been introduced, additional analyses on secondary endpoints may be performed to assess the diagnostic accuracy of pegasitacianine.

The confidence intervals for diagnostic accuracy (e.g. the positive predictive value, negative predictive value, sensitivity, specificity, and true/false negative/positive rate) will also be constructed via a cluster-bootstrap to determine confidence intervals that account for the effects of within-subject clustering. Since the number of specimens each subject has is variable, in order to keep the same number of specimens in the bootstrapped sample, we will cluster initially by the number of specimens each subjects has, and then resampling will occur by first choosing a subject within that cluster and then resampling the same number of specimens they originally had.

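### The 95% intervals attached to sensitivity, specificity, PPV and NPV treat specimens from one patient as independent, and nothing says whether they or the SAP's exploratory clustered intervals govern

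*SAP*

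**What the plan says.** SAP 7.10.2.1, the secondary analysis, computes the four rates at biopsy level for each Group and adds: "Two-sided 95% confidence intervals will be calculated for each rate via Clopper-Pearson method". Protocol 9.4 agrees: "These rates will be reported along with exact two-sided 95% confidence intervals". Neither section mentions clustering.

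Specimens are clustered by design. Protocol 6.3 allows, per patient, 10 suspected-tumor and 5 normal specimens during standard-of-care (SOC) resection: "A total of up to 15 specimens are to be imaged". Guided specimens come on top, and SAP 5.1.2 also brings in nodes: "collected SOC and pegasitacianine guided specimens, as well as lymph nodes, will be compared to histological analyses".

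SAP 7.10.3.3 recognises the correlation and responds in two ways. It will "compare the AUC of the mixed effects ROC curve to the standard ROC curve", and intervals for the same diagnostic rates "will also be constructed via a cluster-bootstrap to determine confidence intervals that account for the effects of within-subject clustering". That bootstrap will "cluster initially by the number of specimens each subjects has", then draw a subject within that stratum and resample the subject's specimens. The section belongs to 7.10.3, Exploratory Analyses.

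SAP 1 says "the SAP will overwrite the protocol with respect to analyses and reporting". This ranks the two documents. It does not choose between two intervals that both stand in the SAP.

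**The concern.** Clopper-Pearson is exact for independent binary outcomes. Specimens from one patient share the tumor, the dose, the operation and the surgeon who calls fluorescence, so their results are likely to be correlated. The interval then claims more information than the data hold.

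As written, each rate will have two different 95% intervals, and the one placed with the secondary endpoints is the one that ignores clustering. Both documents describe a pilot study whose estimates are to serve the power calculations of later studies (Protocol 9.1, SAP 4). Precision is therefore a main product of the trial, and overstated precision would pass into the next design.

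**Working it through.** **Plan's own figure.** The sample size of about 60 comes without a formula, target width or ICC, so there is nothing to reproduce. ICC values below are assumptions.

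**1. Design-effect check.** Inputs from the documents: 60 patients; at most 10 suspected-tumor and 5 normal SOC specimens each; a reference rate of 70%, the Protocol 3.1 threshold for opening Group 2. Assumed: every patient supplies the maximum, and all suspected specimens are tumor. DE = 1 + (m − 1) × ICC, and effective n = n / DE.

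- Sensitivity, m = 10, 420/600: specimen-level Clopper-Pearson gives 0.662 to 0.736. At ICC 0.2, DE = 1 + 9 × 0.2 = 2.8 and effective n = 600 / 2.8 = 214.3. Clopper-Pearson at that size gives 0.634 to 0.761, which is 1.69 times as wide.
- Specificity, m = 5, 210/300: 0.645 to 0.751. At ICC 0.1, DE = 1 + 4 × 0.1 = 1.4 and effective n = 214.3, giving 0.634 to 0.761.
- Simulated coverage of the specimen-level interval at ICC 0.1/0.2/0.3: sensitivity 85.6/77.2/70.8%, specificity 91.2/86.7/82.6%.

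**2. Coverage with uneven specimen counts.** Beta-binomial simulation, 2,000 trials per scenario with 400 bootstrap resamples each. Assumed per subject: 3 to 10 suspected SOC specimens (85% tumor), 1 to 5 normal ones, specificity 75%, and either no guided specimens or 0 to 4. Three methods were compared:

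- Clopper-Pearson on pooled specimens.
- The 7.10.3.3 bootstrap with a percentile interval (the type is assumed; the SAP gives none).
- A cluster-robust logit interval. With y_i successes among m_i specimens in subject i, p = Σy_i / Σm_i, V = Σ(y_i − p·m_i)² / (Σm_i)², and limits logit(p) ± t(k−1) × √V / [p(1 − p)], where k is the number of contributing subjects.

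Coverage for sensitivity (%), at ICC 0.1 / 0.2 / 0.4:

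| Setting | Clopper-Pearson | SAP bootstrap | Robust logit |
|---|---|---|---|
| 40 subjects, 80%, SOC only | 90.4 / 84.9 / 75.6 | 96.6 / 95.6 / 92.8 | 94.8 / 96.0 / 94.8 |
| 60 subjects, 80%, SOC only | 89.6 / 86.0 / 75.1 | 96.9 / 96.8 / 94.5 | 93.9 / 95.8 / 95.2 |
| 40–60 subjects, 95%, all mixes | 90–92 / 85–86 / 76–78 | 94–96 / 92–94 / 87–92 | 94–95 / 94 / 92–94 |
| 10 subjects, 80% | 92 / 84 / 76 | 91–92 / 84–88 / 78–80 | 95–97 / 95–96 / 95 |
| 10 subjects, 95% | 96 / 92–94 / 91–92 | 86–87 / 79–81 / 67–70 | 96–98 where computable |

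The percentage in each row label is the SOC sensitivity. At ICC 0 with 40 to 60 subjects, Clopper-Pearson covers 95 to 97%, so clustering causes the loss. Guided specimens hardly change the 80% rows. For the other rates with 40 to 60 subjects, Clopper-Pearson covers: specificity 91–93/88–91/79–86%, NPV 91–94/89–90/82–83%, PPV 93–95/91–93/85–88%.

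**3. Why the bootstrap weakens in a small Group.** A subject alone in a specimen-count stratum is redrawn every time and adds no between-subject variance. That holds for 40–46% of subjects when a Group has 10, 17–22% at 20, 4–7% at 40 and 2–4% at 60. Where the observed rate is 100%, every resample repeats it and the width is zero. At 10 subjects and 95% sensitivity this happened in 11%, 14–17% and 25–27% of trials. In those trials the logit interval cannot be computed either.

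**4. Price in width.** With 40 subjects, 80% sensitivity and SOC specimens only, mean Clopper-Pearson widths are 0.109/0.109/0.108 and robust widths 0.134/0.155/0.190. The ratios are 0.134/0.109 = 1.23, 0.155/0.109 = 1.42 and 0.190/0.108 = 1.76.

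**The case against.** The strongest reply is that the SAP already deals with clustering. That is largely right. The bootstrap is an unconditional commitment, so a reader who inferred that the analysis is missing, or that it depends on the AUC comparison, would be wrong. The AUC comparison only opens the way to optional further analyses. The word *also* in 7.10.3.3 may simply mean in addition to the ROC check. The tables and figures sit in a separate document that is not available here, and it may settle the display. What stands is narrower: no sentence in the protocol or SAP ranks the two intervals.

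A second reply is that no decision uses these intervals. This too is correct. A reader might infer that opening Group 2 or the primary result is compromised. The documents do not support that: the 70% threshold in Protocol 3.1 applies to point values, SAP 3.1 leaves opening to the sponsor's discretion, and the interval for clinically significant events (CSEs) is computed per subject.

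A third reply is that the size rests on assumptions, and it does. The two checks differ (85.6% against about 90% at ICC 0.1) because their specimen counts and rates differ. With 10 subjects, 95% sensitivity and ICC 0.1, Clopper-Pearson's built-in conservatism even hides the problem.

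It is also tempting to conclude that the bootstrap should simply be promoted. Rates are reported by Group, and the Protocol Summary sets no allocation, so a Group may be small. At an assumed 10 subjects the bootstrap is no real improvement at 80% sensitivity and is clearly worse than Clopper-Pearson at 95%.

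**Conclusion.** The concern holds as a modest defect that should be fixed before database lock. The intervals placed with the secondary endpoints ignore a correlation that the SAP itself recognises, and the clustered intervals have no stated standing. For 40 to 60 subjects and 80% sensitivity, nominal 95% coverage falls to roughly 90/84/75% at assumed ICCs of 0.1/0.2/0.4. The direction is secure for positive correlation at these sizes. The amount is not, because ICC, specimen counts, tumor share and Group sizes are all assumed. Lymph nodes were not modelled, since no count is given; more specimens per patient would increase the effect.

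The AUC comparison cannot settle the matter. It looks for bias in a summary of accuracy, and two similar AUCs would say nothing about interval width.

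The robust interval is not perfect either: at 95% sensitivity and ICC 0.4 with 40 to 60 subjects it covers 92–94%. Across the settings examined it is still the most dependable of the three.

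**What to change.** In SAP 7.10.2.1, before database lock:

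1. Name one reported 95% interval for each diagnostic rate, by Group and overall: the cluster-robust logit-scale interval, clustered on subject (GEE with independence working correlation, or the equivalent ratio variance), with t on k − 1 degrees of freedom, where k is the number of subjects contributing to that rate. State any small-sample variance factor.
2. Keep the 7.10.3.3 bootstrap as a sensitivity analysis, not as the governing per-Group interval. State its interval type, number of resamples and seed.
3. Keep specimen-level Clopper-Pearson as a companion labelled *assumes independent specimens*. Use it alone, with that label, where the observed rate is exactly 0% or 100% and the logit interval cannot be computed.
4. State that the AUC comparison does not bear on interval width.
5. Leave the subject-level Clopper-Pearson interval for CSEs unchanged.
6. Record the change in SAP 8. A protocol amendment appears unnecessary, because SAP 7.1 asks for one only where primary conclusions may be affected.

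The cost is a few sentences and one standard procedure, with no new data. The reported sensitivity intervals become about 20%, 40% and 75% wider at ICC 0.1, 0.2 and 0.4 (40 subjects, 80% sensitivity), and keep about the same width at ICC 0.

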7.10.3 Exploratory Analyses

7.10.3.1 Analysis of Fluorescence Intensity

A summary of MFI for the tumor (or suspected tumor), MFI for the normal background tissue, and TBR will be provided by Group and pathology result (tumor vs. no tumor). This summary will be at the specimen level, meaning each subject may have multiple specimens.

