9.5 Quantification of Fluorescence Intensity

Specimen-to-background (SBR) ratios and tumor-to-background (TBR) ratios will also be calculated using white light and NIR images of both SOC and pegsitacianine guided specimens. SBRs will be calculated using *ex situ* images of collected specimens. The equation for calculating SBR is listed below.

$$\text{SBR} = \frac{\text{Mean Fluorescence Intensity (Specimen)}}{\text{Mean Fluorescence Intensity (Normal Tissue)}}$$

TBR is calculated in the same way, but refers specifically to samples that are histologically confirmed as tumor.

The mean fluorescence intensity of the specimen, of the background, and the SBR (or TBR) of each specimen will be summarized by the histologically-confirmed tumor status (either “tumor present” or “tumor not present/normal tissue”).

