2. STUDY OBJECTIVES

2.1 Objectives and Endpoints

The main objective of this study is to investigate whether pegsitarcianine can detect residual disease in the peritoneal cavity following standard of care (SOC) resection of peritoneal metastases using a [REDACTED] mg/kg dose administered [REDACTED] prior to surgery.

Table 1. Objectives and Endpoints

Objectives	Endpoints
Primary Objective	Primary Endpoint

The primary objective of this study is to determine if administration of pegasitacianine (█ mg/kg) results in the detection of metastatic disease left behind following standard of care surgical resection of peritoneal metastases.
	
Rate of detection of disease left behind following SOC resection of peritoneal metastases as measured by rate of Clinically Significant Events (CSEs).

Secondary Objectives	Secondary Endpoints

Demonstrate reliable sensitivity, specificity, negative predictive values (NPPV), and positive predictive values (PPV) of the imaging agent at the level of the individual specimens.
	
Sensitivity, specificity, negative predictive values (NPV), and positive predictive values (PPV).

Demonstrate an acceptable safety profile.	Incidence of TEAEs and SAEs, abnormalities in lab values, vital signs, or ECG results.
Exploratory Objectives	Exploratory Endpoints
Assess the how the normalized SBR value affects the diagnostic accuracy of pegsitacianine in detection of metastatic disease vs. normal tissue.	ROC analysis across various specimen-to-background ratio fluorescence thresholds.
Effect of camera system on diagnostic results.	Diagnostic results across various camera systems.
Assess amount of fluorescence shown in various types of specimens.	Mean fluorescence intensity and Specimen-to-background ratio

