5.1.3 Fluorescence Endpoints

Specimen-to-background (SBR) ratios will also be calculated using white light and NIR images of both SOC and pegsitacianine guided specimens. SBRs will be calculated using *ex situ* images of collected specimens. The equation for calculating SBR is listed below.

$$\text{SBR} = \frac{\text{Mean Fluorescence Intensity (Specimen)}}{\text{Mean Fluorescence Intensity (Normal Tissue)}}$$

Note, Tumor-to-background (TBR) ratios are equivalent to SBR, but only relevant for specimens with tumors.

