7.10.3.2 ROC Analysis

In this pilot study we are assuming that any fluorescence is indicative of tumor presence. To assess how the amount of observed fluorescence (e.g., the SBR or TBR) may affect the diagnostic accuracy of pegasitacianine, a receiver operating characteristic (ROC) analysis will be performed on all specimens using the observed thresholds of SBR and TBR. The corresponding ROC curve will be provided along with the area under the curve (AUC).

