7.10.3.4 Camera System Analysis

An analysis on diagnostic results by camera system will be performed. 2x2 incidence tables comparing the true/false negative/positive results will be constructed for each camera system, and compared via the Breslow-Day test to assess if there is any effect of camera system on diagnostic results (e.g. to test if the common odds-ratio of each incidence table is equivalent across camera types). A summary including the diagnostic true/false negative/positive numbers and rates for each camera system, sensitivity, specificity, and p-value of this analysis will be provided.

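### MFI summaries and the SBR ROC are not separated by camera system, and TBR is named where only SBR is defined

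*SAP*

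**What the plan says.** **Intensity summary.** SAP 7.10.3.1: "A summary of MFI for the tumor (or suspected tumor), MFI for the normal background tissue, and TBR will be provided by Group". The same sentence adds a second split, by whether histology found tumour. Camera system is not a stratifier and SBR is not named, although SAP 2.1 gives the matching exploratory endpoint as "Mean fluorescence intensity and Specimen-to-background ratio".

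**ROC.** SAP 7.10.3.2 has the analysis "performed on all specimens using the observed thresholds of SBR and TBR", with no camera stratum or covariate.

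**Cameras.** SAP 2.1 lists the endpoint "Diagnostic results across various camera systems". SAP 7.9.5 includes the camera among the surgery details summarised per patient and listed. SAP 7.10.3.4 applies a Breslow-Day test "to assess if there is any effect of camera system on diagnostic results", but only to true/false positive/negative counts. MFI, SBR and AUC have no camera analysis. SAP 7.6 also excludes centre differences.

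**TBR.** SAP 5.1.3 says that tumour-to-background "ratios are equivalent to SBR, but only relevant for specimens with tumors". Protocol 9.5 agrees: "TBR is calculated in the same way, but refers specifically to samples that are histologically confirmed as tumor".

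**The concern.** The plan treats a camera effect as a real question for the yes/no result, but not for the continuous measures, which lie closest to the device. A mean fluorescence intensity depends on the gain of the system that produced it, and the visible text describes no gain, exposure or calibration rule. Protocol 6.3 fixes the field width at 10 cm and the in-situ camera distance at 15 cm, which does not put different cameras on one intensity scale. If cameras also differ by more than gain, one SBR threshold is not the same test on each.

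At stake is the exploratory objective on how SBR relates to diagnostic accuracy. In addition, the two sections ask for a TBR in specimens that have none by definition, so a programmer cannot follow them literally.

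**Working it through.** The documents state no AUC, MFI, SBR or gain figure, so there is nothing to reproduce. The numbers below only show how the mechanism works.

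**Inputs from the documents.** SBR = specimen MFI / normal-tissue MFI (SAP 5.1.3, Protocol 9.5). The SOC target for each patient is up to 10 suspected tumour and 5 normal specimens (Protocol 6.3).

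**Assumptions, none from the documents.** Two cameras, A and B, with equal numbers of specimens; within-camera SBR AUC 0.85; true tumour/no-tumour mean ratio 2.08; tumour share either equal across cameras or 80% on one and 50% on the other.

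**1. MFI, with camera B at 5 times the gain of A.**
- Equal tumour share: both means are multiplied by (1 + 5)/2 = 3. The ratio stays 2.08, but the pooled means (7.40 and 3.56 in simulation) belong to neither camera's scale.
- B has 80% tumour, A 50%: B supplies 0.8/1.3 = 0.615 of tumour and 0.2/0.7 = 0.286 of non-tumour specimens. The multipliers are 0.615×5 + 0.385 = 3.46 and 0.286×5 + 0.714 = 2.14. The pooled ratio is 2.08 × 3.46/2.14 = 3.36 (3.35 in simulation).
- Shares reversed: 0.385×5 + 0.615 = 2.54 and 0.714×5 + 0.286 = 3.86. The pooled ratio is 2.08 × 2.54/3.86 = 1.37.

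**2. SBR with a pure gain difference.** Gain g cancels: gS/gB = S/B. Pooled AUC stays 0.85 in every mix.

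**3. SBR with an uncorrected offset o in one camera.** SBR becomes (S + o)/(B + o), which is pulled towards 1. With o equal to the median background signal, simulation (200,000 specimens per camera) gives a pooled AUC of 0.84 with equal tumour share, 0.82 if the offset camera has the higher share, and 0.86 if it has the lower.

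**4. SBR with a general shift of s SD in log SBR.** Tumour/normal separation is d = √2 × z(0.85) = 1.414 × 1.036 = 1.466. With equal tumour share, half of all tumour/normal pairs cross cameras:

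AUC = 0.5·Φ(d/√2) + 0.25·Φ((d + s)/√2) + 0.25·Φ((d − s)/√2)

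- s = 0.5: 0.843
- s = 1: 0.5×0.850 + 0.25×0.959 + 0.25×0.629 = 0.822
- s = 2: 0.761

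With shares of 80% and 50% and s = 1, same-camera pairs are 0.615×0.286 + 0.385×0.714 = 0.451 of the total. Cross-camera pairs are 0.615×0.714 = 0.440 (tumour on the high-share camera) and 0.385×0.286 = 0.110 (the reverse).
- High-share camera reads high: 0.451×0.850 + 0.440×0.959 + 0.110×0.629 = 0.874.
- High-share camera reads low: 0.451×0.850 + 0.440×0.629 + 0.110×0.959 = 0.765.

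**5. One threshold, s = 1, equal tumour share.** Put the cut-off midway, at d/2 + s/2 = 1.233. Sensitivity/specificity is Φ(0.233)/Φ(1.233) = 59%/89% on one camera and 89%/59% on the other, against Φ(d/2) = 77%/77% with no shift. The pooled AUC falls only to 0.82, so it would largely hide this.

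**6. Stratifying.** An AUC built from within-camera pairs only returns 0.85 in each scenario.

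**7. TBR.** Under SAP 5.1.3 and Protocol 9.5 the no-tumour TBR cell in 7.10.3.1 is empty, and a TBR ROC in 7.10.3.2 has no negatives, so neither specificity nor AUC exists. If TBR is computed as SBR, its curve is the SBR curve again.

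**The case against.** The case for leaving the plan alone has several sound parts.

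- **The sizes are assumed.** This stands. A 1 SD camera shift is 1/1.466 = 68% of the assumed tumour/normal separation, and 2 SD is 136%. Nothing in the documents supports shifts that large in a ratio that already cancels gain.
- **Tumour share is probably similar across cameras.** The common 10:5 target pushes that way, and equal shares can only lower the AUC. Post-SOC specimens and final pathology can still make the shares differ.
- **There is a partial safeguard.** SAP 7.10.3.3 compares the standard ROC with a mixed-model ROC clustered by subject, and camera is summarised at patient level, so a subject effect can absorb part of a camera shift. In a simulation of 60 patients (10 tumour and 5 normal specimens each, two cameras, logistic random intercept), a 2 SD shift gave a pooled AUC of 0.76 against 0.84 from the mixed model; 1 SD gave 0.82 against 0.83. The SAP does not specify the model, so the protection is real but uncertain, and it does nothing for MFI.
- **Calibration may be described elsewhere.** The camera operating instructions and Imaging Workbook are not part of these documents. One can say only that the visible text describes no calibration.
- **TBR is loose labelling.** Protocol 9.5 and the listing in SAP 7.10.2.1 both write SBR or TBR, which suggests the intended reading. That makes the correction easy, but it is still needed.

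A reader might infer that the ROC will set a cut-off for later studies. The documents do not say so: their stated forward use is to inform power calculations.

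**Conclusion.** The point holds, within limits. MFI, SBR and the ROC are not separated by camera although several systems are expected. Pooled MFI has no common scale if gains differ without calibration. The pooled SBR AUC may be distorted if cameras differ by more than gain. With equal tumour shares that means attenuation; movement in either direction requires unequal shares. The actual size is unknown, and every AUC above is conditional on the stated assumptions.

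A reader might infer that the planned AUC is biased, in either direction. The documents do not support that, because they give no evidence of offset, saturation or non-linearity, or of tumour share differing by camera. Nor does the TBR wording bias anything: it leaves one table cell and one curve either undefined or a duplicate.

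The consequence is confined to exploratory, descriptive output. The primary CSE endpoint and the binary sensitivity and specificity use neither MFI nor SBR. The change is still worth making, because it is cheap and serves a stated objective.

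**What to change.** - **SAP 7.10.3.1:** present MFI and SBR by camera system, within Group and pathology result, and do not rely on pooled MFI.
- **SAP 7.10.3.2:** keep the pooled SBR ROC. Add a camera-stratified AUC that uses only tumour/normal pairs imaged on the same camera, and by-camera AUCs where numbers allow.
- **Both sections:** replace TBR with SBR wherever non-tumour specimens are included.

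The cost is SAP wording and extra table rows from data already collected. The drawback is sparse cells: with about 60 patients split by Group, pathology and camera, a rarely used system may support only counts or a listing. If the cameras agree, the stratified and pooled AUCs will be close and nothing is lost.
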